1.4 Target Population, Sample Size and Study Duration

Approximately 3000 participants from the States of Michigan and Ohio who meet the study entry criteria will be prospectively enrolled and randomized at Henry Ford Health System (a member of the Detroit COVID Consortium). Future protocol amendments may expand the geographic areas from which patients are drawn and add additional enrolling sites. The fourth non-randomized comparator arm will include participants that are already on chronic HCQ maintenance therapy with weight-based, twice a day dosing for their autoimmune disease, which will be continued throughout the study. Enrollment in this group will be open as it will be a non-randomized treatment arm; the total number of participants enrolled in this group is expected to be lower than in the randomized groups. Total study duration is expected to be up to 2 years, with participant enrollment starting in April 2020.

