2.1 Case report forms (CRFs)

Case report forms (CRFs) that use Participants' study identifiers are designed and developed for the trial according to CDISC foundational standards as required for FDA-regulated trials. CRFs will be approved by the Trial PI. The DCC will work closely with the Trial PI and Biorepository Core to identify pre-analytic and analytic data elements to ensure data and specimen reproducibility and quality.

Due to the urgency for trial recruitment during the COVID pandemic period, paper CRFs were prepared and used in the beginning of study when the CRF database was not ready for the trial data entry. Trial recruitment began on April 10th using the paper CRFs.

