2.2 Database management system for study data collection

The DCC has implemented a centralized, integrated electronic data capture (EDC) system—comprised of RedCAP, SQL, and Forte EDC data management systems—for trial data and sample collection and management: (1) RedCap is used to collect pre-screening data for possible eligible participants; (2) SQL is used for registering and tracking study samples; and (3) Forte EDC, an FDA 21 CFR Part 11-compliant data management system, is used for trial CRF data collection.

The DCC has prepared a data dictionary and all CRF fields will have consistent variable names to ensure accurate coding. A detailed Data Collection manual of procedures (MOP) has been prepared by the DCC as part of the training material for the clinical sites. The DCC will be responsible for training study staff in EDC as well as how to apply the MOP for CRF completion. The DCC will also provide a CRF data-quality and data-monitoring plan as part of the study documentation.

In general practice, a DCC CRF database should be ready prior to study enrollment. However, given the urgency for trial recruitment during the COVID pandemic period, paper CRFs were prepared and used before the Forte EDC database was built, validated and released on 4/17/2020. In addition, RedCap was used as an interim system to assist clinical sites for participant recruitment and study enrollment, and for the AE and SAE tracking log, until the Forte EDC database was up and running and clinical site staff were trained for CRF data entry. The RedCap AE and SAE tracking log was discontinued on 5/14/2020 when the Forte EDC AE and SAE tracking system was fully implemented. *To be able to enroll subjects elsewhere beside HFHS and to incorporate the study protocol revision to include pregnant women, a Forte EDC V2 database was implemented and went live on 7/26/2020 for new patient enrollment. The V1 database is referred to as the original database, which retained all patients enrolled prior to 7/26/2020 including their follow-up data collection. The V2 database has a revised CRF data cluster structure which is about 70% similar to the original Forte database (named V1 CRF data cluster, see Table in Appendix A). As a result, data quality checks are conducted separately for each version of the Forte database. The data will be integrated for analysis using SAS.*

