Secondary Hypothesis (S7): There is an HCQ dose effect on AEs and SAEs, compared to placebo.

The endpoint will be any AE and any SAE observed during the 8 weeks of follow-up after enrollment.

Safety Analysis Set is considered by including all randomized subjects.

A descriptive analysis will report AE frequency and grade distribution among the three arms, and include a detailed list of serious adverse events (SAEs).

S8: To examine other clinical determinants contributing to the risk of SARS-CoV 2 infection including demographics, work type and location, positive COVID-19 partners, possible exposures and clinical symptoms.

Secondary Hypothesis (S8): Risk for SARS-CoV 2 infection varies by subject demographics, work type and location, and clinical conditions.

The possible covariates will include subject demographics, work type and location, and clinical conditions at the baseline prior to study enrollment, as well as the study treatment status. The endpoint will be clinical COVID-19 disease confirmed by laboratory test (same endpoint as P1).

FAS is considered. Logit univariate and multivariate modeling will be conducted with consideration of possible treatment-by-baseline covariate interaction. Variables will be retained in the final model if there is significant individual effect or variable-by-treatment interaction at p-value 0.05. Area under the receiver operating characteristic curve (AUROC) will be used to assess the predictive ability.

S9: To examine the association between HCQ drug levels and development of COVID-19 symptoms or positive test results.

Secondary Hypothesis (S9): There is an association between HCQ drug levels and development of COVID-19 symptoms or positive test results.

The endpoint will be the same, as described for S1 *using FAS*.

A similar analysis as that described for S1 will be used. The analysis will include concentration of HCQ in blood at baseline, week 4 and week 8 as covariates.

S10: To identify immunologic, serological and inflammatory markers associated with acquisition and response to COVID-19 in both HCQ and placebo Participants developing laboratory or clinical confirmed disease.

Secondary Hypothesis (S10): There are immunologic, serological and inflammatory markers for COVID-19 positive.

Two separate endpoints, SARS-CoV 2 test positive, and COVID19 disease with SARS-CoV 2 test positive laboratory confirmation (P1), will be considered.

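### S8 does not pre-specify calendar time of enrolment, so its work-type, work-location and baseline-condition associations may be confounded by period

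*SAP*

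**What the plan says.** SAP 6.3.4.4 gives the S8 covariates as follows: "The possible covariates will include subject demographics, work type and location, and clinical conditions at the baseline prior to study enrollment". Study treatment is added in the same sentence. The outcome is the primary endpoint, clinical COVID-19 with laboratory confirmation, analysed in the full analysis set.

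On the model: "Logit univariate and multivariate modeling will be conducted with consideration of possible treatment-by-baseline covariate interaction". On selection: "Variables will be retained in the final model if there is significant individual effect or variable-by-treatment interaction at p-value 0.05". The baseline variables identified in S8 are then included in S10.

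On timing, SAP 2.1 states: "Trial recruitment began on April 10th using the paper CRFs". SAP 2.2 reports that "a Forte EDC V2 database was implemented and went live on 7/26/2020 for new patient enrollment", and gives the purpose: "To be able to enroll subjects elsewhere beside HFHS and to incorporate the study protocol revision to include pregnant women". Protocol 6.2.2 excludes pregnant and nursing participants, so the documents describe pregnancy as becoming eligible through a later revision.

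Follow-up is 8 weeks per participant (SAP 6.1). The SAP's population (1.1 and 1.3) is wider than that of the supplied protocol: it adds medical students, household family members of healthcare workers, transit drivers generally and Ohio. No dates are given for these additions. No section of the SAP uses enrolment date, calendar period or community incidence as an adjustment.

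**The concern.** A participant's chance of infection in an 8-week window depends on when that window falls in the epidemic. A logistic model for the whole window has no time axis, so it cannot see this unless a calendar term is put in.

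In the arm comparisons this does no harm, because participants are randomised to all three arms concurrently within site. S8 is different: it contrasts groups that nobody randomised. If one work group, work location or baseline condition tends to enrol later than another, and incidence has moved in the meantime, enrolment period is an ordinary confounder of the contrast.

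At stake is what S8 is for, namely saying who is at higher risk. A period difference could pass the 0.05 retention rule and be reported as an occupational or clinical determinant.

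**Working it through.** S8 states no sample size, effect size or power, so it has no figure to reproduce. The check has three parts.

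**1. Dates.** From 10 April to 26 July 2020 is 20 + 31 + 30 + 26 = 107 days, or 15.3 weeks. Follow-up is 56 days. Since 107 − 56 = 51, anyone enrolled up to about 31 May had reached the planned end of follow-up before the second database opened. Early enrolees and those enrolled through the new database were therefore at risk in non-overlapping periods.

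**2. Size of a false association, by hand.** Assumed inputs, not document figures: early 8-week risk 10%; later risk varied; no true difference between groups; group A enrols 80% early, group B 20% early. Crude risk = share early × 0.10 + share late × later risk.

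| Later risk | A | B | Odds ratio, A v B |
|---|---|---|---|
| 8% | 9.6% | 8.4% | 1.16 |
| 5% | 9.0% | 6.0% | 1.55 |
| 3% | 8.6% | 4.4% | 2.04 |
| 1% | 8.2% | 2.8% | 3.10 |

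For the 3% row: (0.086/0.914)/(0.044/0.956) = 2.04. If B enrols only late, its risk is 3.0% and the odds ratio is (0.086/0.914)/(0.030/0.970) = 3.04. If the later risk is also 10%, or the two groups have the same share early, the odds ratio is 1.

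**3. Chance of passing the 0.05 rule, and the effect of a period term.** Inputs from SAP 6.4: rates of 10% on placebo and 6.8% on hydroxychloroquine, giving an average of (0.10 + 2 × 0.068)/3 = 7.87%; 900 + 1800 = 2,700 analysed. (As a check on these inputs, the SAP's 82% power for 1,800 v 900 reproduces at 81.6%.) Assumed: 300 of the 2,700 belong to a group enrolled only late, 30% of the others also enrol late, the true odds ratio is 1, and the test is two-sided. Logistic models with treatment and group were fitted to 1,000 simulated trials per row, with and without an early/late term.

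| Late/early incidence | Median OR, no period term | p<0.05 | p<0.05 with period term |
|---|---|---|---|
| 1 | 0.99 | 5% | 5.2% |
| 0.75 | 0.80 | 9% | 3.5% |
| 0.5 | 0.57 | 42% | 4.7% |
| 2 | 1.63 | 76% | 4.8% |

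With the period term the median odds ratio is 0.99 to 1.00 in every row.

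A closed-form Wald calculation gives the wider range, with 150 to 600 in the late group and 0 to 60% of the others enrolling late:
- incidence ratio 0.5: odds ratio 0.48 to 0.70, significant in 13% to 90%;
- ratio 0.75: 0.73 to 0.88, 7% to 37%;
- ratio 2: 1.30 to 2.19, 20% to 100%.

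The closed form is somewhat generous: for the simulated scenario it gives 14%, 44% and 82% where the simulation gives 9%, 42% and 76%.

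**The case against.** The strongest objection is that the documents do not show the confounding to be present. A reader might infer that new work groups and sites joined months into the epidemic, so that S8 will misread the epidemic curve as an occupational or site effect. The text does not support that:

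- Only the opening of the second database is dated. Medical students, family members, other transit drivers and Ohio carry no dates. The SAP mentions protocol versions of 04/16/2020 and 05/26/2020, which are 6 and 46 days after recruitment began, and these groups could have entered then.
- SAP 1.4 still describes enrolment at Henry Ford and treats more sites as a possibility: "Future protocol amendments may expand the geographic areas from which patients are drawn and add additional enrolling sites". Nothing confirms that another site enrolled.
- Location in the protocol synopsis is the participant's main work area. Enrolling site is a randomisation stratum, not a listed S8 covariate.
- Healthcare workers, nursing home workers, first responders and Detroit bus drivers were all eligible under the supplied protocol, and no difference in timing among them is shown.
- Neither document gives incidence over time.

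All of this stands, and it limits the point to a risk of bias.

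Two further objections carry less weight. The covariates are only called possible, so calendar time is not prohibited. But SAP 6.3.4.1 makes analyses that are not described and are run after lock post hoc and exploratory, which is a reason to name the term now. It may also be said that S10 is not shown to suffer, because a work-type term standing in for period would partly adjust for period there. That is fair, and no harm to S10 is claimed; carrying the term forward is a matter of consistency.

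**Conclusion.** The point holds as a gap in pre-specification. S8 compares non-randomised groups over 8-week windows in a recruitment that spanned at least 107 days, and it names no calendar term. Pregnancy is the clearest dated case of a baseline condition tied to later enrolment, if S8 uses it as a covariate.

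Bias requires both a change in incidence and a difference in enrolment timing between the groups compared. If both occur, a false odds ratio of about 1.2 to 3 is possible under the assumed rates. A modest change (incidence ratio 0.75) raises the false-positive rate only from 5% to 9% in the simulated scenario. The hand calculation gives crude odds ratios, and the simulated model adjusts only for treatment; the full S8 model could give somewhat different values.

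The primary analysis and the other randomised comparisons are untouched. This is a low-cost improvement to a secondary, observational aim.

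**What to change.** Amend S8 in SAP 6.3.4.4 before database lock:

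1. Include calendar month of enrolment (or a wider period, with cut-points fixed in advance) in the univariate and multivariable S8 models, exempt from the 0.05 retention rule. Carry it into S10.
2. Tabulate enrolment dates by work group, work location and the main baseline conditions, so that readers can see whether timing differed.
3. If more than one region enrols, allow the period term to differ by region, since one common term assumes the same epidemic course everywhere.
4. State that where a group has no overlap in enrolment time with the others, its effect cannot be separated from period, and report it as such.

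The data are to hand: Protocol 8.1 already requires the consent date. The cost is a few degrees of freedom and wider intervals for groups enrolled late. At the planning rates about 0.0787 × 2,700 = 212 events are expected, enough for a handful of month terms; if events prove scarce, use fewer, wider periods. Item 4 is a limit that the adjustment cannot remove.

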## 1 BACKGROUND

Community-acquired pneumonias (CAPs) can be due to viral or bacterial pathogens, and are one of the most common infectious diseases. Viral CAPs are most commonly caused by influenza A and B and other common cold viruses such as RSV, especially during winter months. Although their presentations can vary, only microbiological testing techniques can definitively identify the pathogen involved. In December 2019, a novel disease caused by a new virus now known as SARS-CoV-2, commonly referred to as COVID-19, was identified in Wuhan, China. Since then, the infection has spread worldwide, with over 663,828 cases identified and 30,822 deaths as of March 28, 2020 (Johns Hopkins Coronavirus Resource Center, <https://coronavirus.jhu.edu/map.html>). COVID-19 is a deadly pandemic which threatens the lives of millions of persons with mortality rates overall of 4.37%, but are highly very variable by region. For example, in Italy a crude mortality rate of 10.83% has been reported. In the United States, over 124,217 cases and 2,185 deaths have been reported, with the State of Michigan now representing the fourth most affected state, having 4,658 confirmed cases and 111 deaths reported (Johns Hopkins Coronavirus Resource Center, March 28, 2020; <https://coronavirus.jhu.edu/map.html>). HCW are at high risk of exposure given the close proximity in which they care for patients (Bureau of Labor Statistics, Occupational Employment Statistics) in addition to the growing shortages in personal protective equipment (PPE), which are paralleling the rise in COVID-19 cases (1,2). Recent COVID-19 outbreaks have demonstrated that up to 10-30% of HCW can become infected by the virus, and up to 85% may have asymptomatic/minimally symptomatic infection, promoting further spread of COVID-19 infection (2). Several epidemiological, societal and clinical interventions are currently ongoing to prevent the spread of COVID-19 disease, but to date, there are no published data on prevention strategies. This is a critical unmet need which must be addressed to preserve the population of active healthcare workers (HCW), nursing home workers (NHW), DDOT bus drivers, and first responders (FR) who are exposed to COVID-19 positive patients as part of their duties and represent the key component of our clinical response to this pandemic.

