6.3 Study Aims, Hypothesis and Proposed Analysis

6.3.1 Primary Aim and Hypothesis

As noted below, the primary aim has been changed to: (based on Study Protocol dated 05/26/2020)

To determine if the use of hydroxychloroquine as preventive therapy decreases the rate of acquisition of SARS-CoV 2 infections [with clinical COVID-19 disease](#) in Study Participants [for each randomized treatment arm](#) as compared to placebo.

From: (based on original Study Protocol, dated at and after 04/06/2020)

To determine if the use of hydroxychloroquine as preventive therapy decreases the rate of acquisition of SARS-CoV 2 infections in Study Participants as compared to placebo.

Primary Hypothesis (P1): Hydroxychloroquine administered daily decreases the rate of acquisition of SARS-CoV 2 infections with clinical COVID-19 disease, compared to placebo; and hydroxychloroquine administered weekly decreases the rate of acquisition of SARS-CoV 2 infections with clinical COVID-19 disease, compared to placebo.

The **primary outcome** will be defined as clinical COVID-19 disease with laboratory confirmation of infection.

Presentation with COVID-19 symptoms during study follow-up (defined as fever $\geq 38^{\circ}$ C, or two or more non-fever symptoms that are new since the baseline) will refer participants to obtain SARS-CoV 2 testing through employee health or participants' primary care physician, with test results documented in their medical record.

Laboratory confirmation of SARS-CoV 2 infection (SARS-CoV 2 test positive) will be defined as at least one positive RT PCR, or both IgM and IgG positive serology. The lab test results can be obtained from (a) study blood samples (IgM and IgG serology), and (b) RT PCR test results ordered by a participant's primary care physician or through employee health.

All participants who test SARS-CoV 2 positive will be followed for at least 30 days after the first positive test for presentation of symptoms.

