FAS is considered. The immunologic, serological and inflammatory markers will be collected using the baseline blood samples. The same analysis approach as described for S8 will be used for S10. The baseline variables identified from S8 will be included for S10 analysis.

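### S8 asks what determines SARS-CoV-2 infection, but its only endpoint is symptomatic laboratory-confirmed disease, so asymptomatic infections count as non-cases and symptom-related factors can pass as infection determinants

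*SAP*

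**What the plan says.** The S8 aim, given in Protocol 2.2 (item 8), SAP 1.2 (item 8) and SAP 6.3.4.4, is "To examine other clinical determinants contributing to the risk of SARS-CoV 2 infection including demographics, work type and location". Its hypothesis is "Risk for SARS-CoV 2 infection varies by subject demographics, work type and location, and clinical conditions". The endpoint that follows is "The endpoint will be clinical COVID-19 disease confirmed by laboratory test (same endpoint as P1".

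P1, the primary outcome in SAP 6.3.1, "will be defined as clinical COVID-19 disease with laboratory confirmation of infection". Laboratory confirmation there means "at least one positive RT PCR, or both IgM and IgG positive serology". Symptoms during follow-up "will refer participants to obtain SARS-CoV 2 testing through employee health" or the participant's own physician; the other laboratory source is serology on study blood.

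The documents keep infection and disease apart elsewhere. The Protocol's Abbreviations/Definitions describe infection as laboratory detection, whether or not symptoms are present. Protocol 2.5 lists infections among the secondary outcomes, separately from the primary disease outcome. SAP S1 sorts participants into three categories: (1) not test positive, (2) test positive without symptoms, (3) test positive with symptoms.

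S10 models two endpoints, test-positive status and P1, by the S8 method, but "The baseline variables identified from S8 will be included for S10 analysis".

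**The concern.** S8 is run in the full analysis set, so a participant in S1 category 2 is not dropped. That person is infected by the Protocol's definition and is analysed with the uninfected.

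To become a P1 case, a participant must be infected, develop symptoms, and be tested. A baseline factor associated with any of these steps can meet S8's 0.05 retention rule, and the S8 hypothesis would then have it reported as affecting the risk of infection. Demographics and baseline clinical conditions, both S8 covariates, could plausibly act on symptoms rather than on infection. Work type could also affect access to testing.

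The variables S8 retains then become the adjustment set for S10, including S10's test-positive model. A factor related to infection but not retained on P1 is not carried forward, while one related only to symptoms is. No other planned analysis selects demographic, work or exposure factors on an infection endpoint.

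The mismatch may date from the revision of the primary aim recorded in SAP 6.3.1, from infection to infection with clinical disease. An S8 endpoint tied to P1 would have matched its aim before that change. This is an inference; the SAP does not say so.

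**Working it through.** **Inputs**

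- Placebo disease rate 10%, average HCQ disease rate 6.8% (SAP 6.4).
- Analysable size 900 or 935 per arm (SAP 6.4; 935 is the size chosen for the revised aim).
- Background infection range in healthcare workers, up to 10-30% (Protocol 1).
- Asymptomatic share of detected infections: not given in the SAP. The Protocol background has only "up to 85% may have asymptomatic/minimally symptomatic infection".
- Assumed: symptomatic share *s*, taken as equal in all arms for the counts.

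**Step 1. The plan's own figure.** S8 has no stated power, so this checks only the rates used below. SAP 6.4 gives 82% for 10% v 6.8% with 900 placebo and 1,800 pooled HCQ. With a pooled null standard error of 0.01099, an unpooled one of 0.01163 and two-sided alpha 0.0497 (z = 1.9625): (0.032 - 1.9625 × 0.01099) / 0.01163 = 0.897, a power of 81.5%. A two-look simulation of the pooled test gives 81.9%, against 0.819 in SAP Table 1. The figure reproduces.

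**Step 2. Expected P1 events.**
- 900 per arm: 900 × 0.10 + 1,800 × 0.068 = 212.4 of 2,700.
- 935 per arm: 935 × 0.10 + 1,870 × 0.068 = 220.7 of 2,805 (7.9%).

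**Step 3. Infections coded as non-cases.** Infections = events / *s*; misclassified = infections - events; placebo infection rate = 10% / *s*. At 935 per arm:

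| *s* | Placebo infection | Infections | Coded as non-cases |
|---|---|---|---|
| 1.0 | 10.0% | 221 | 0 |
| 0.7 | 14.3% | 315 | 95 |
| 0.5 | 20.0% | 441 | 221 |
| 0.33 | 30.3% | 669 | 448 |

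Holding placebo disease at 10% and placebo infection within 10-30%, the asymptomatic share runs from 1 - 0.10/0.10 = 0% to 1 - 0.10/0.30 = 67%. It passes one half only if placebo infection exceeds 20%. At *s* = 0.5 the misclassified are 221 / (2,805 - 221) = 8.6% of S8's non-cases (212 / 2,488 = 8.5% at 900 per arm).

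**Step 4. What S8 estimates.** With infection risk *r* and symptomatic share *s*, the P1 risk is *rs* (confirmation taken as complete), and the odds ratio compares *rs*/(1 - *rs*) between groups. The risks and shares here are illustrative.

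- *Factor acting on infection only*, *r* = 10% v 20%, same *s*. Infection odds ratio: (0.20/0.80)/(0.10/0.90) = 2.25. P1 odds ratio: 2.16 at *s* = 0.7, 2.11 at 0.5, 2.07 at 0.33 and 2.03 at 0.15. The risk ratio is 2.0 throughout.
- *Factor acting on symptoms only*, *r* = 20% in both groups, *s* = 30% v 60%. Infection odds ratio 1.0. P1 risks are 6% and 12%, odds ratio (0.12/0.88)/(0.06/0.94) = 2.14. With shares of 40% v 60% it is 1.57.

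**Step 5. Power for an infection-only factor.** Prevalence 50%, risk ratio 1.3, 2,805 participants, two-sided 0.05. The lower-risk group has risk 2 × average / 2.3. On P1 (average 7.9%) power is 52%. On infection it is 69% at *s* = 0.7, 85% at 0.5 and 97% at 0.33.

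**The case against.** The strongest reply is that P1 contains infection. If the symptomatic share does not vary with a factor, its P1 risk ratio equals its infection risk ratio, so for pure exposure factors S8 loses mainly power. Step 4 confirms this, and the point stands. A reader might infer that S8 estimates determinants of showing symptoms, or that it cannot address infection at all. Neither follows: determinants of symptoms would need a model among the infected, and infection-only factors remain visible on P1.

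A reader might also infer from the 85% in the Protocol background that S8 discards most of the infections the trial will detect. The documents do not support that. Nobody is discarded. The 85% is an upper limit that pools asymptomatic with minimally symptomatic infection, and some of the latter could meet P1: two new non-fever symptoms already trigger referral, and positives are followed at least 30 days for symptoms. Combined with 10% placebo disease, 85% implies 10% / 0.15 = 67% placebo infection, outside the 10-30% in the same background section. SAP 6.4 also uses the same 10% placebo rate for infection (original aim) and for disease (revised aim), which gives no support for a large asymptomatic excess.

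Two further replies have force. Test-positive status is not a clean measure of infection either, since PCR follows symptoms while asymptomatic infection is found mainly if study blood is positive for both IgM and IgG. And S10 does model test-positive status, while S1, S2 and S9 separate asymptomatic positives. That narrows the gap without closing it, because S10's non-marker covariates are selected on P1. Using that adjustment set does not by itself make S10 invalid.

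**Conclusion.** The mismatch is explicit in the text: an infection aim and hypothesis, a disease endpoint, and asymptomatic positives analysed as non-cases. What S8 delivers is determinants of symptomatic, laboratory-confirmed infection.

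The consequence depends on the factor. Infection-only factors are found with slight attenuation of the odds ratio and lower power. Factors acting only on symptoms or testing would be mislabelled. The 2.14 shows the mechanism under assumed shares; it is not a forecast.

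The number misclassified cannot be fixed from the documents. The 0% to 67% range rests on combining the planned 10% placebo disease rate with a background range that is not tied to this trial's eight weeks. The figure of 212 to 221 holds at a 50% asymptomatic share. The primary efficacy test is unaffected. This is a secondary analysis that should be corrected because its conclusions, as worded, would go beyond its endpoint.

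**What to change.** 1. Make test positive during follow-up the S8 endpoint: S1 categories 2 and 3 combined, against category 1.
2. Keep P1 as a second S8 model, labelled as determinants of clinical disease. S10 already uses this pairing.
3. In S10, adjust each endpoint for the baseline variables selected on that same endpoint.
4. State with the results that PCR is prompted by symptom referral and that asymptomatic infection is found mainly through study serology, so test-positive status remains partly symptom-driven.

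The cost is SAP wording and one extra model. S1 already derives the endpoint, so no new data are needed. The change should be made before database lock, since SAP 6.3.4.1 treats later additions as post hoc.

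At minimum, if P1 alone is kept, reword the S8 aim, hypothesis and conclusions to symptomatic laboratory-confirmed disease. That resolves the mismatch but leaves determinants of infection unexamined.
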